#### **8.4.5.3. Occupational Exposure**

The investigator must report any instance of occupational exposure to Pfizer Safety within 24 hours of the investigator's awareness using the PSSA, regardless of whether there is an associated SAE. Since the information about the occupational exposure does not pertain to a participant enrolled in the study, the information is not recorded on a CRF; however, a copy of the completed SAE Case Report from PSSA must be maintained in the investigator site file.

#### **8.4.6. Cardiovascular and Death Events**

Not applicable.

#### **8.4.7. Disease-Related Events and/or Disease-Related Outcomes Not Qualifying as AEs or SAEs**

Not applicable.

#### **8.4.8. Adverse Events of Special Interest**

Not applicable.

##### **8.4.8.1. Lack of Efficacy**

The investigator must report signs, symptoms, and/or clinical sequelae resulting from lack of efficacy. Lack of efficacy or failure of expected pharmacological action is reportable to Pfizer Safety **only if associated with an SAE**.

#### **8.4.9. Medical Device Deficiencies**

Not applicable.

#### **8.4.10. Medication Errors**

Medication errors may result from the administration or consumption of the study intervention by the wrong participant, or at the wrong time, or at the wrong dosage strength.

Medication errors are recorded and reported as follows:

Recorded on the Medication Error Page of the CRF	Recorded on the Adverse Event Page of the CRF	Reported Using the PSSA to Pfizer Safety Within 24 Hours of Awareness
All (regardless of whether associated with an AE)	Any AE or SAE associated with the medication error	Only if associated with an SAE

Medication errors include:

- Medication errors involving participant exposure to the study intervention;
- Potential medication errors or uses outside of what is foreseen in the protocol that do or do not involve the study participant.
- The administration of expired study intervention;
- The administration of an incorrect study intervention;
- The administration of an incorrect dosage;
- The administration of study intervention that has undergone temperature excursion from the specified storage range, unless it is determined by the sponsor that the study intervention under question is acceptable for use.

Such medication errors occurring to a study participant are to be captured on the medication error page of the CRF, which is a specific version of the AE page.

Whether or not the medication error is accompanied by an AE, as determined by the investigator, the medication error is recorded on the medication error page of the CRF and, if applicable, any associated AE(s), serious and nonserious, are recorded on the AE page of the CRF.

In the event of a medication dosing error, the sponsor should be notified within 24 hours.

Medication errors should be reported to Pfizer Safety within 24 hours using PSSA **only when associated with an SAE**.

### **8.5. Pharmacokinetics**

A blood sample of approximately 1 mL, to provide approximately 0.5 mL plasma, will be collected for measuring plasma concentrations of nirmatrelvir and ritonavir (if feasible) as specified in the [SoA](#).

Instructions for the collection and handling of biological samples will be provided in the laboratory manual or by the sponsor. The actual date and time (24-hour clock time) of each sample will be recorded.

The actual times may change, but the number of samples will remain the same. All efforts will be made to obtain the samples at the exact nominal time relative to dosing. Collection of the baseline sample obtained <30 min later than the 1-2 hour post-dose timepoint will not be captured as a protocol deviation, as long as the exact time of the collection is noted on the source document and the CRF. This protocol deviation does not apply to samples that are specified to be collected “at any time”.

PK samples may be collected at any time during the visit on Days 5, 10, and 15. PK samples collected within the allowed visit window schedule will not be captured as a protocol deviation.

Samples collected for analyses of ninnatrelvir and ritonavir concentrations may also be used to evaluate safety or efficacy aspects related to concerns arising during or after the study, for metabolite identification and/or evaluation of the bioanalytical method or for research related to the study intervention and COVID-19 CCI [REDACTED]

If a participant cannot attend in-clinic visits, PK samples may be collected via home health or mobile visit. The time of PK samples being taken will be recorded.

Genetic analyses will not be performed on these plasma samples unless consent for this was included in the informed consent. Participant confidentiality will be maintained.

Samples collected for measurement of plasma concentrations of study intervention will be analyzed using a validated analytical method in compliance with applicable SOPs. Potential metabolites may be analyzed with either validated or exploratory methods.

The PK samples must be processed and shipped as indicated in the instructions provided to the investigator site to maintain sample integrity. Any deviations from the PK sample handling procedure (eg, sample collection and processing steps, interim storage, or shipping conditions), including any actions taken, must be documented, and reported to the sponsor. On a case-by-case basis, the sponsor may make a determination as to whether sample integrity has been compromised.

Dmg concentration information that would unblind the study will not be reported to investigator sites or blinded personnel until the study has been unblinded.

Any changes in the timing or addition of time points for any planned study assessments must be documented and approved by the relevant study team member and then archived in the sponsor and site study files, but will not constitute a protocol amendment. The IRB/EC will be informed of any safety issues that require alteration of the safety monitoring scheme or amendment of the ICD.

## **8.6. Genetics**

### **8.6.1. Specified Genetics**

Specified genetic analyses are not evaluated in this study.

### **8.6.2. Retained Research Samples for Genetics**

Retained Research Samples will be collected from adult participants only; these samples will not be collected from participants who are under the age of 18 at the time of enrollment.

A 4-mL blood sample optimized for DNA isolation Prep D1 will be collected according to the [SoA](#), as local regulations and IRBs/ECs allow.

Retained Research Samples may be used for research related to the study intervention(s) and COVID-19. Genes and other analytes (eg, proteins, RNA, nondmg metabolites) may be studied using the retained samples.

See [Appendix 5](#) for information regarding genetic research. Details on processes for collection and shipment of these samples can be found in the laboratory manual.

### 8.7. Biomarkers

Collection of samples for biomarker research is also part of this study.

The following samples for biomarker research are required and will be collected in this study as specified in the [SoA](#):

- **CCI** [REDACTED]

I [REDACTED]

I [REDACTED]

I [REDACTED]

[REDACTED]

[REDACTED]

Residuals of all samples may be stored for future research. Storage and shipping instructions will be in accordance with the laboratory manual.

**CCI** [REDACTED]

[REDACTED]

Residuals of all samples may be stored for future research. Storage and shipping instructions will be in accordance with the laboratory manual.

CCI [REDACTED]

Details on processes for collection and shipment of these samples can be found in the laboratory manual and supporting documents.

#### 8.7.6. Specified Metabolomic Research

Specified metabolomic research is not included in this study.

#### 8.7.7. Retained Research Samples for Biomarkers

These Retained Research Samples will be collected in this study:

- CCI [REDACTED]

I [REDACTED]

I [REDACTED]

Retained Research Samples will be collected as local regulations and IRB/ECs allow according to the [SoA](#). Retained Research Samples will be collected from adult participants only; these samples will not be collected from participants who are under the age of 18 at the time of enrollment.

Retained Research Samples may be used for research related to the study intervention(s) and COVID-19. Genes and other analytes (eg, proteins, RNA, nondrug metabolites) may be studied using the retained samples.

See [Appendix 5](#) for information regarding genetic research. Details on processes for collection and shipment of these samples can be found in the laboratory manual.

## 8.8. Immunogenicity Assessments

Immunogenicity assessments are not included in this study.

## 8.9. Health Economics

Health economics/medical resource utilization and health economics parameters will be evaluated for this study ([Section 8.2.2](#) and [Section 8.2.4](#)).

## 9. STATISTICAL CONSIDERATIONS

Detailed methodology for summary and statistical analyses of the data collected in this study is outlined here and further detailed in the SAP, which will be maintained by the sponsor. The SAP may modify what is outlined in the protocol where appropriate; however, any major modifications of the primary endpoint definitions or their analyses will also be reflected in a protocol amendment.

The efficacy and safety data will be analyzed and summarized separately for the main study population and the additional population with rebound. Further details on the analyses planned for the additional population with rebound will be included in the SAP.

There will be 2 analysis time points for reporting the results of this study. The primary analysis will be performed after all participants in the main study population have completed the Day 44 visit. The follow-up analysis will be performed after all participants in the main study population have completed the Week 24 visit. In addition, both analyses (primary and follow-up) will include separate results for the main study population and the additional population with rebound.

### 9.1. Statistical Hypotheses

No formal hypothesis testing will be performed for this study.

#### 9.1.1. Estimands

##### 9.1.1.1. Primary Estimand/Coprimary Estimands

The primary estimand, reported separately for the main study population and the population with rebound, is the proportion of participants with sustained NP swab SARS-CoV-2 RNA <LLOQ (defined as <2.0 log10 copies/mL) from Day 15 through Day 44 in nonhospitalized, symptomatic patients ≥12 years of age with COVID-19 who are immunocompromised. This will be estimated without regard to study treatment discontinuation and considering participants receiving non-study antiviral or monoclonal antibody therapy post-baseline for the treatment of COVID-19 as not achieving sustained NP swab SARS-CoV-2 RNA <LLOQ.

##### 9.1.1.2. Secondary Estimands

Not Applicable.

### 9.1.2. Multiplicity Adjustment

There will be no adjustment for multiplicity.

### 9.2. Analysis Sets

For purposes of analysis, the following analysis sets are defined and will be applied for the main study population and the population with rebound:

Participant Analysis Set	Description
Full analysis set	All participants randomly assigned to study intervention.
Evaluable analysis set/Safety Analysis Set	All participants randomly assigned to study intervention and who take at least 1 dose of study intervention.

The evaluable analysis set will be the primary analysis set for evaluating the primary estimand.

### 9.3. Statistical Analyses

The SAP will be developed and finalized before any analyses are performed and will describe the analyses and procedures for accounting for missing, unused, and spurious data. This section is a summary of the planned statistical analyses of the primary and secondary endpoints.

#### 9.3.1. General Considerations

Descriptive statistics for all endpoints will be provided by treatment arm.

The number of participants screened, completing the study drug administration, and completing the study will be summarized. The reason for all discontinuations will be summarized.

Baseline demographic and other characteristics will be tabulated for the FAS.

For continuous endpoints, descriptive statistics for change from baseline will be provided.

For binary endpoints, the proportion of participants with the event will be summarized.

For categorical endpoints, the proportion of participants for each category will be summarized.

### 9.3.2. Primary Endpoint(s)/Estimand(s) Analysis

#### 9.3.2.1. Definition of Endpoint(s)

The primary endpoint, summarized separately for the main study population and the population with rebound, is the proportion of participants with sustained NP swab SARS-CoV-2 RNA <LLOQ (defined as <2.0 log10 copies/mL) from Day 15 through Day 44.

Sustained is defined as NP swab SARS-CoV-2 RNA level not  $\geq 2.0$  log10 copies/mL at any study visit (through Day 44) following the first study visit where the participant's NP swab SARS-CoV-2 RNA <LLOQ.

#### 9.3.2.2. Main Analytical Approach

The primary descriptive analysis will summarize, separately for the main study population and the population with rebound, the number and proportion of participants with sustained NP swab SARS-CoV-2 RNA <LLOQ (defined as <2.0 log10 copies/mL) from Day 15 through Day 44 for each treatment arm in the Evaluable Analysis Set and FAS. Participants receiving non-study antiviral or monoclonal antibody therapy post-baseline for the treatment of COVID-19 will be considered as not achieving sustained NP swab SARS-CoV-2 RNA <LLOQ in the primary analysis. In addition, 95% CIs for the proportion of participants with sustained NP swab SARS-CoV-2 RNA <LLOQ from Day 15 through Day 44 for each treatment arm will be calculated. The difference in proportions for the primary endpoint and associated 95% CI will be calculated for each pairwise comparison of the treatment arms.

#### 9.3.2.3. Supplementary Analysis/Analyses

Supplemental analyses will be performed for the primary efficacy endpoint:

1. An analysis of the primary endpoint will be conducted excluding data after the date of non-study antiviral or monoclonal antibody start for participants receiving non-study antiviral or monoclonal antibody therapy post-baseline for the treatment of COVID-19.
2. An analysis of the primary endpoint will be conducted to include all NP swab SARS-CoV-2 RNA data regardless of whether participants received non-study antiviral or mAb treatment post-baseline for the treatment of COVID-19.

### 9.3.3. Secondary Endpoint(s)/Estimand(s) Analysis

Details on the definitions and analyses of secondary endpoints will be described in the SAP. Secondary endpoints include:

- Time to first NP swab SARS-CoV-2 RNA <LLOQ (<2.0 log10 copies/mL) for participants with NP swab SARS-CoV-2 RNA  $\geq$ LLOQ at baseline.
- Time to sustained NP swab SARS-CoV-2 RNA <LLOQ (<2.0 log10 copies/mL) through Day 44 for participants with NP swab SARS-CoV-2 RNA  $\geq$ LLOQ at baseline.

- Proportion of participants with SARS-CoV-2 RNA <LLOQ in plasma over time.
- Proportion of participants with SARS-CoV-2 RNA level in NP swabs <2.0 log10 copies/mL at each study visit through Day 44.
- Change from baseline in SARS-CoV-2 RNA level in NP swabs and in plasma over time.
- Rebound in SARS-CoV-2 RNA level in NP swabs at follow up (ie, any study visit after end of treatment through Day 44) that is defined as a half (0.5) log10 copies/mL increase or greater in SARS-CoV-2 RNA level relative to end of treatment SARS-CoV-2 RNA level based on treatment regimen, with a follow-up viral RNA level ≥2.5 log10 copies/mL.
- Incidence of TEAEs.
- Incidence of SAEs and AEs leading to discontinuations.
- Proportion of participants with COVID-19-related hospitalization >24 hours, or death from any cause through Day 28.
- Proportion of participants with death (all cause) through Week 24.
- Proportion of participants with COVID-19-related hospitalization of any duration.
- Proportion of participants with COVID-19-related ICU admission of any duration.
- Proportion of participants requiring invasive mechanical ventilation or ECMO.
- Number of days in hospital and ICU stay in participants with COVID-19-related hospitalization.
- Number of COVID-19-related medical visits through Day 44 and through Week 24.
- Duration of each targeted COVID-19 signs/symptoms.
- Proportion of participants with severe signs/symptoms attributed to COVID-19 through Day 44.
- Nirmatrelvir and ritonavir PK in plasma and whole blood (if feasible).

#### **9.3.4. Tertiary/Exploratory Endpoint(s) Analysis**

- Not applicable.

#### **9.3.5. Safety Analyses**

All safety analyses will be performed on the safety analysis set.

### 9.3.6. Other Analyses

Pharmacogenomic and/or biomarker data from samples collected as described in the SoA, as well as Retained Research Samples may be retained for future analyses; the results of such analyses are not planned to be included in the CSR.

Rates of detection of cell culture infectious virus over time will be characterized during the trial and will be reported in a separate report outside of the CSR.

PRO data (SF-36, WPAI, EQ-5D-5L, and global impression questions) will be collected during the trial and are not planned to be included in the CSR.

Results from population PK analyses will be reported in a separate report outside of the CSR.

### 9.4. Interim Analyses

No formal interim analysis will be conducted for this study.

### 9.5. Sample Size Determination

Up to approximately 200 participants will be enrolled in this study.

The study will randomize approximately 150 participants in a 1:1:1 randomization ratio, resulting in approximately 50 participants in each treatment arm (main study population). In addition, the study will also enroll up to 50 additional nonhospitalized symptomatic participants (in a 1:1:1 randomization ratio) who are immunocompromised with a rebound in COVID-19 within 14 days following completion of an initial 5-day treatment course of nirmatrelvir/ritonavir (population with rebound).

Analyses will be conducted after the main study population is fully enrolled and have completed the Day 44 visit regardless of the number of randomized participants in the population with rebound. There will be 2 analysis time points for reporting the results of this study. The primary analysis will be performed after all participants in the main study population have completed the Day 44 visit. The follow-up analysis will be performed after all participants in the main study population have completed the Week 24 visit. In addition, both analyses (primary and follow-up) will include separate results for the main study population and the additional population with rebound.

As no formal hypothesis testing will be performed for this study, no power calculation was carried out to assess the number of participants required for each treatment arm. For the main study population, the goal of the primary analysis is to estimate the treatment effect for each duration of nirmatrelvir/ritonavir. The smaller numbers of participants in these groups will be reflected in the precision of the estimate of the primary endpoint. Table 2 displays which effect sizes would be excluded based on the expected width of the confidence interval around the estimate of the proportion of participants with sustained NP swab SARS-CoV-2 RNA <LLOQ (defined as <2.0 log10 copies/mL) from Day 15 through Day 44 with a sample size of 50.

When the proportion of participants with sustained NP swab SARS-CoV-2 RNA <LLOQ from Day 15 through Day 44 ranges from 0.1 to 0.5, Table 2 displays the precision (width of the confidence interval) for the respective proportion to be estimated with a sample size of 50. That is, the width of the 95% CI does not exceed 14%.

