**Table 2. Width of 95% CI for the Proportion of Participants with Sustained NP Swab SARS-CoV-2 RNA <LLOQ**

Nirmatrelvir/Ritonavir (n=50)	
Proportion of Participants With Sustained Viral RNA level <LLOQ	Width of CI
0.1	0.083
0.2	0.111
0.3	0.127
0.4	0.136
0.5	0.139

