Table 2.Width of 95% CI for the Proportion of Participants with Sustained NP
Swab SARS-CoV-2 RNA <LLOQ	Nirmatrelvir/Ritonavir (n=50)		
Proportion of Participants With Sustained Viral	Width of CI	
RNA level <lloq< th="">	</lloq<>		
0.1	0.083	
0.2	0.111	
0.3	0.127	
0.4	0.136	
0.5	0.139	

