6.1.1. Main Analysis

The primary descriptive analysis will summarize, separately for the main study population and the population with rebound, the number and proportion of participants with sustained NP swab SARS-CoV-2 RNA <LLOQ (defined as <2.0 log₁₀ copies/mL) from Day 15 through Day 44 for each treatment arm in the Evaluable Analysis Set and FAS. Participants DMB02-GSOP-RF02 7.0 *Statistical Analysis Plan Template* 31-Jan-2022

> PFIZER CONFIDENTIAL TMF Doc ID: 98.03 Page 16 of 32

receiving non-study antiviral or monoclonal antibody therapy post-baseline (between randomization and Day 44 visit) for the treatment of COVID-19 will be considered as not achieving sustained NP swab SARS-CoV-2 RNA <LLOQ in the primary analysis.

As viral load measurements from NP swabs are taken on Days 15, 21, 28, 35, and 44 during the time interval from Day 15 to Day 44, all of the measurements that are non-missing must be <LLOQ (including undetectable), and the Day 15, Day 44, and no more than one of the Day 21, 28, and 35 measurements can be missing in order for the event to be considered sustained.

In addition, 95% CIs for the proportion of participants with sustained NP swab SARS-CoV-2 RNA <LLOQ from Day 15 through Day 44 for each treatment arm will be calculated using binomial distribution normal approximation. The difference in proportions for the primary endpoint and associated 95% CI will be calculated for each pairwise comparison of the treatment arms.

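### Table 2 labels 95% CI half-widths as widths: at n=50 the full width is 16.6 to 27.7 percentage points, not at most 14

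*Protocol*

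**What the plan says.** Protocol 9.5 plans about 50 participants in each arm of the main study population. It says that, with no hypothesis to test, power was not calculated. In its place the section offers a precision statement: "Table 2 displays the precision (width of the confidence interval) for the respective proportion to be estimated with a sample size of 50". For proportions between 0.1 and 0.5 it concludes: "That is, the width of the 95% CI does not exceed 14" per cent. It also tells the reader that the table shows which effect sizes the interval would rule out.

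Table 2 is titled "Width of 95% CI for the Proportion of Participants with Sustained NP Swab", with a column again labelled as the width of the CI. The entries are 0.083, 0.111, 0.127, 0.136 and 0.139 for proportions of 0.1, 0.2, 0.3, 0.4 and 0.5.

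SAP 2.4 repeats the text and the table ("Width of 95% CI for the Proportion of Participants with Sustained NP"). Neither document describes these values as a half-width, a margin of error or a ± quantity. SAP 6.1.1 says the 95% interval for each arm's proportion will be "calculated using binomial distribution normal approximation", and SAP Appendix 1 says the same. The Protocol names no interval method.

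**The concern.** A 95% interval for a proportion with 50 participants cannot be as narrow as 14 percentage points from end to end when the proportion lies between 0.1 and 0.5. The tabulated values look like one arm of the interval, reported as if they were the whole of it.

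This matters because Table 2 is the only quantitative support either document gives for 50 per arm. Read as written, it promises twice the precision the design has. It also affects the sentence about excluded effect sizes. A reader who takes 0.139 as the full width would think that an observed 0.5 excludes true values of 0.40 or 0.60, and it does not. The intervals in the study report will then be about twice as wide as the plan led readers to expect.

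**Working it through.** **Inputs.** n = 50 per arm and p = 0.1 to 0.5 (Protocol 9.5; SAP 2.4). Two-sided 95% confidence, z = 1.96 (1.959964 in the calculation). Normal approximation to the binomial (SAP 6.1.1).

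**Step 1: reproduce the table.** Half-width h = z × √(p(1−p)/n). For p = 0.5: 1.96 × √(0.25/50) = 1.96 × 0.0707 = 0.1386. All five entries match to three decimals.

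**Step 2: full width.** Upper limit minus lower limit = 2h.

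| p | Table 2 | h | Full width 2h | 95% limits p ± h |
|---|---|---|---|---|
| 0.1 | 0.083 | 0.0832 | 0.166 | 0.017 to 0.183 |
| 0.2 | 0.111 | 0.1109 | 0.222 | 0.089 to 0.311 |
| 0.3 | 0.127 | 0.1270 | 0.254 | 0.173 to 0.427 |
| 0.4 | 0.136 | 0.1358 | 0.272 | 0.264 to 0.536 |
| 0.5 | 0.139 | 0.1386 | 0.277 | 0.361 to 0.639 |

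Even the smallest full width, 16.6 points at p = 0.1, exceeds the stated ceiling of 14.

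**Step 3: could another interval make the label true?** Full 95% widths at n = 50, from p = 0.1 to p = 0.5:

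- Wilson: 0.170 to 0.267
- Agresti-Coull: 0.179 to 0.267
- Exact (Clopper-Pearson): 0.185 to 0.29

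None comes near 0.083 to 0.139. A normal-approximation interval at 90% confidence does not either (0.140 to 0.233).

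**Step 4: what the label would require.**

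- An interval at p = 0.5 with full width 0.139 extends 0.0695 each side, or 0.0695/0.0707 = 0.98 standard errors. Its confidence level is about 67%.
- A 95% interval no wider than 0.14 at p = 0.5 needs n = 4 × 1.96² × 0.25 / 0.14² = 196 per arm.
- Matching each tabulated value as a full width needs about 199 to 201 per arm, four times the planned 50.

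**Step 5: effect on interpretation at an observed 0.5.** Literal label: 0.5 ± 0.139/2 = 0.43 to 0.57. Planned analysis: 0.5 ± 0.139 = 0.36 to 0.64.

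**The case against.** The best defence is that nothing was miscalculated and nothing depends on the label. The study has no hypothesis test, no multiplicity adjustment and no interim analysis. No target precision is stated from which 50 was derived, so correcting the label leaves no design requirement unmet. The study report will show real intervals computed by the SAP method. An experienced statistician would probably recognise 0.139 as a ± margin, because a full width that small is impossible at n = 50. Used that way, the table excludes the right values.

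Most of this stands, and it limits the seriousness of the error. It does not remove it. The prose sentence, the table title and the column header all say width, in both documents, and no other text corrects them. Readers who are not statisticians have no reason to reinterpret the word. Nothing shows that anyone has been misled, so the fair statement is that the sentence on excluded effect sizes may be misread, not that it has been.

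**Conclusion.** The concern holds. The tabulated values are half-widths. The full 95% CI widths at n = 50 run from 16.6 to 27.7 percentage points, so the claim of at most 14 is wrong at every tabulated proportion and overstates precision by a factor of two. This is an error of labelling, with one false conclusion drawn from it, in the only precision statement supporting the sample size. It should be corrected, but it does not call the sample size, the analysis or the reported intervals into question.

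The figures assume exactly 50 participants per arm contribute to the proportion. Fewer would widen the interval further; SAP 4 removes one site from the efficacy analyses and SAP 5.3 lets the denominator shrink with missing data. For the Protocol, the interval method is inferred from the exact match of all five values and from the SAP. Step 3 shows that the conclusion does not depend on that inference.

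**What to change.** In Protocol 9.5 with its Table 2, and in SAP 2.4 with its Table 2:

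- Retitle the table and its column as *Half-width (±) of 95% CI*, and carry the new title into each document's list of tables.
- In the sentence introducing the table's precision, replace *width* with *half-width*.
- Restate the conclusion: the half-width is at most 14 percentage points, so the full interval spans up to about 28 points.
- In the sentence on excluded effect sizes, replace the expected width with the expected half-width, and say that the interval for a single arm is the estimate ± that value.

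Doubling the tabulated values and giving a maximum of about 28 points would serve equally well, provided the text and table agree. The cost is wording in a few places in each document, with no change to sample size, analysis or outputs. The stated precision becomes less favourable, but it will match the intervals the study reports.
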